13.0 STUDY ADMINISTRATION

13.1 **Investigator's Brochure**

Before the study begins, the Investigator will receive the OR-421a IB describing all known nonclinical data, contraindications, warnings, precautions, and adverse reactions associated with the administration of the study drug. If such information is revised while the study is in progress, the IB will be amended or revised, and the Sponsor will provide the most current version to the Investigator.

Protocol Amendments 13.2

If there are any substantial changes to the study protocol, these changes will be documented in a protocol amendment and in a new version of the protocol. The Sponsor will inform the Investigator in writing of any amendment to the protocol. The Investigator must submit the protocol modifications and any ICF modifications to the IRB/EC, and approval must be obtained before the modifications are implemented. The Investigator must send a copy of the approval letter from the IRB/EC to the Sponsor for review. The Investigator may implement a deviation from, or a change of, the protocol to eliminate an immediate hazard(s) to subjects without prior IRB/IEC approval/favorable opinion. In this case, as soon as possible, the implemented deviation or change, the reasons for it, and, if appropriate, the proposed protocol amendment(s) should be submitted to the sponsor, IRB/EC and if applicable the regulatory authority.

ProQR Therapeutics Page 53 of 65

13.3 **Study Termination**

Both the Sponsor and the Investigator reserve the right to terminate the study according to the study contract. The Investigator should notify the IRB/EC in writing of the study's completion or early termination and send a copy of the notification to the Sponsor.

If the Sponsor, Medical Monitor or designee, study center monitor, or appropriate regulatory officials discover conditions arising during the study that indicate that the study should be halted or that a study center should be terminated, this action may be taken after appropriate consultation. Termination may occur in accordance with the clauses contained in the study center's executed clinical study agreement. The Sponsor reserves the right to discontinue the study prior to enrollment of the intended number of subjects but intends only to exercise this right for valid scientific reasons.

If the clinical development of QR-421a is discontinued, the Sponsor shall immediately inform all Investigators/institutions and regulatory authorities. Study termination and follow-up will be performed in compliance with the conditions set forth in the ICH Guidelines S7A (ICH 2000) and local regulatory requirements.

13.4 **Study Documentation and Storage**

The Sponsor will provide the Investigator with records of drug shipments, eCRFs, and other forms as necessary. The Investigator and study staff are responsible for maintaining a comprehensive and centralized filing system of all study-related documentation, suitable for inspection at any time by representatives from the Sponsor and/or applicable regulatory authorities. Elements should include, but are not limited to:

- Subject files containing ICFs and supporting originals of source documentation.
- Study files containing the protocol with all amendments, IB, copies of pre-study documentation, and all correspondence to and from the IRB/EC, applicable country authorities, and the Sponsor.
- Records of drug accountability and all drug-related documentation.

In addition, all original source documents supporting entries in the eCRFs must be maintained and be readily available.

Upon the request of the Sponsor, designees, or the regulatory authorities, the Investigator will make all study records available for inspection, including source documents. This information will be treated as confidential.

No study document is to be destroyed without prior written agreement between Sponsor and the Investigator. Should the Investigator wish to assign the study records to another party or move them to another location, he/she must notify the Sponsor in writing of the new responsible person and/or the new location.

ProQR Therapeutics Page 54 of 65

13.5 Use of Information

All personal data pertaining to the subjects in this study and in any subsequent reports will be kept confidential. Subjects will be identified only by their month and year of birth and a subject number. It is the responsibility of the Investigator to keep a subject listing for cross-referencing.

The sponsor will notify the Member States concerned about a serious data security breach at the time of the breach without undue delay but not later than 7 days of becoming aware of that breach. Measures that will be implemented to mitigate the possible adverse effects of a serious data security breach include, but are not limited to, back-ups including remote location, high availability systems for critical environments, and a security incident response plan.

The Investigator understands that the information developed in the clinical study will be used by the Sponsor in connection with the development of the study drug. This information may be disclosed to other clinical Investigators, to the US FDA, and to other government agencies.

Biological samples remaining after the tests described in this protocol are completed, may be used for additional research purposes. This additional research may be done by or on behalf of the Sponsor, to increase overall knowledge on QR-421a, and the effects of QR-421a on RP due to exon 13 mutations of the USH2A gene as well as the effect on other diseases. The samples may be stored or used for as long as they last or are needed for research.

The Sponsor will ensure that personal data transfers and bodily materials transfer comply with Data Protection Laws of the EU, ie, the General Data Protection Regulation 2016/679. To that end, all parties/vendors involved in this study will have been assessed and qualified by the Sponsor to ensure data privacy protection is at an adequate level. Appropriate contractual arrangements (Standard Contractual Clauses) will be in place and sufficient supplement technical measures will be implemented by the parties involved in the study.

13.6 **End of Study and Final Report**

Last Patient Last Visit defines the date that the last subject completed the study. The End of the Study is the date of the Last Patient Last Visit.

The Investigator or delegate must notify the IRB/EC upon study completion or termination in compliance with local regulations.

The Sponsor or its designee will provide a final report and/or synopsis to the Investigators, the IRB/EC and Regulatory Authorities in accordance with local requirements.

13.7 **Financing and Insurance**

Financing and Insurance are addressed separately in the Clinical Study Agreement.

ProQR Therapeutics Page 55 of 65

13.8 **Publication Policy**

Publication policy is addressed separately in the Clinical Study Agreement.

Page 56 of 65 **ProQR Therapeutics**

16.0 APPENDICES

ProQR Therapeutics Page 61 of 65 24 May 2022

ProQR Therapeutics
Page 62 of 65
24 May 2022

ProQR Therapeutics
Page 63 of 65
24 May 2022

ProQR Therapeutics
Page 64 of 65
24 May 2022

16.2 APPENDIX 2: CLINICAL LABORATORY TESTS

Chemistry	Hematology	Urinalysis (dipstick)
Sodium	Hematocrit	Color and appearance
Potassium	Hemoglobin	Specific gravity
Chloride	Red blood cells	pН
Bicarbonate	White blood cells (WBCs)	Protein
Blood urea nitrogen (BUN)	Neutrophils	Glucose
Creatinine	Lymphocytes	Blood (erythrocytes)
Glucose	Monocytes	Leukocytes
Calcium	Eosinophils	Bilirubin
Phosphorus	Basophils	Ketones
Albumin	Platelets	Nitrite
Total protein		Urobilinogen
Alkaline phosphatase (ALP)		
Aspartate aminotransferase (AST)		
Alanine aminotransferase (ALT)		
Gamma-glutamyl transferase (γGT)		
Total and direct bilirubin		
Lactic dehydrogenase (LDH)		
Creatinine clearance (eGFR by		
CKD-EPI)*		
C-reactive protein (CRP)		
Other Tests		Coagulation
Pregnancy testing		INR
		Prothrombin time

^{*} Estimated eGFR is to be calculated using the Chronic Kidney Disease Epidemiology Collaboration CKD-EPI Creatinine Equation 2009 calculation for adult subjects and Schwartz equation, according to the recommendation from National Institutes of Health/National Institute of Diabetes and Digestive and Kidney Diseases, for pediatric subjects

1. ABBREVIATIONS

Abbreviation	Definition
AD	Analysis Description
AE	Adverse Events
AESI	Adverse Event of Special Interest
BCVA	Best Corrected Visual Acuity
CE	Contralateral Eye
CSR	Clinical Study Report
ETDRS	Early Treatment Diabetic Retinopathy Study
ICF	Informed Consent Form
ICH	International Council on Harmonization
LLVA	Low Luminance Visual Acuity
MedDRA	Medical Dictionary for Regulatory Activities
MH	Medical History
PT	Preferred Term
RP	Retinitis Pigmentosa
RTF	Rich Text Format
SAE	Serious Adverse Event
SAP	Statistical Analysis Plan
SD-OCT	Spectral Domain Optical Coherence Tomography
SOC	System Organ Class
TE	Treated Eye
TEAE	Treatment Emergent Adverse Event
TLF	Table Listing Figure format
WHO	World Health Organization

2. INTRODUCTION AND STUDY OBJECTIVES

2.1. Introduction

Study PQ-421a-002 (Helia) aimed to evaluate the safety, tolerability, and efficacy of ultevursen in subjects with Retinitis Pigmentosa (RP) due to mutations in exon 13 of the *USH2A* gene. This open-label, extension study allowed subjects who have participated in ultevursen clinical studies to continue to receive treatment or follow up, and to observe the long-term safety, tolerability, systemic exposure, and efficacy. This open-label extension study also allowed for treatment of the previously untreated contralateral eye (CE; if applicable).

2.2. Study Termination

In this context, the Analysis Description (AD) is abbreviated and describes the populations for analysis, data handling rules, statistical methods, and formats for data presentation that will be required for the close out of the study, after all subjects have completed the end of study visit and the database is locked.

The summary tabulations and listings that will be produced for the close out of the study, will provide the basis for the appropriate sections of the abbreviated clinical study report (CSR) or equivalent document.

3. STUDY DESIGN

3.1. Synopsis of Study Design

PQ-421a-002 is an open-label, extension study to evaluate the safety, tolerability, and efficacy of QR-421a in subjects with RP due to mutations in exon 13 of the *USH2A* gene. Subjects who participated in a preceding ultevursen clinical studies will be given the opportunity to participate in this extension study for continued dosing, provided the subject's benefit-risk assessment is positive, or for additional follow up.

Definition of the Treatment Eye and Contralateral Eye in Helia

Contralateral eye (CE)/Fellow eye is defined as follows: For subjects previously dosed (active or sham) in the preceding ultevursen study: the eye that was not selected as the treated eye (TE). For subjects that were not dosed at all: the eye with the worst BCVA at Helia Screening/Day1.

Treated eye (TE)/Study eye is defined as follows: For subjects previously dosed (active or sham) in the preceding ultevursen study: the eye that was selected as the TE. For subjects that were not dosed at all: the eye with the best BCVA at Helia Screening/Day1.

3.2. Analysis Groups by Eye

For analyses performed at the eye level, the TE and the CE will be grouped separately into the following analysis groups within each analysis set.

- i. Ultevursen 180 µg/60 µg: a dosing regimen consisting of a 180 µg loading dose and a maintenance dose of 60 µg every 6 months during the HELIA study.

- ii. Ultevursen 60 µg / 60 µg: a dosing regimen consisting of a maintenance dose of 60 µg every 6 months (without a 180 µg loading dose) during the HELIA study.
- iii. All eyes: all TE or CE in the analysis set, depending on the eye for analysis

3.3. Analysis Groups by Subject

For analyses performed at the subject level, subjects will be grouped into the following analysis groups within each analysis set as follows. Subject-level analyses will include subjects who received the specified treatment in either eye:

- Ultevursen 180 ug/60 µg: receipt of a dosing regimen consisting of a 180 µg loading dose and a maintenance dose of 60 µg every 6 months in the HELIA study in the TE, CE or both.
- Ultevursen 60 ug/60 µg: receipt of a dosing regimen consisting of a 60 µg loading dose and a maintenance dose of 60 µg every 6 months in the HELIA study in the TE, CE or both. These subjects **never** received the ultevursen 180 ug/60 µg dosing regimen in any eye.
- All subjects: all subjects in the analysis set.

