2.2.1 Nonclinical Experience

ProQR Therapeutics
Page 18 of 65
24 May 2022

2.2.2 **Clinical Experience**

The clinical development program started in the first half of 2019 with the first-in-human (FIH) clinical study (PQ-421a-001), a Phase 1b/2, double-masked, sham-controlled, dose-escalation study to evaluate the safety and tolerability of QR-421a. An interim analysis was performed in March 2021 and the final participant visit was in Q4 2021. The study is undergoing final analyses and reporting.

Available safety and efficacy data from study PQ-421a-001 support the therapeutic potential observed in the nonclinical studies. Reference is made to the IB for further details.

2.3 **Benefit Risk Assessment**

RP is a group of inherited eye disorders causing photoreceptor degeneration, leading to progressive vision loss. Affected patients first experience defective dark adaption, peripheral visual field loss when photoreceptor degeneration progresses, and eventually have only a residual central island of vision, which ultimately progresses to complete blindness. There are currently no approved therapies for the treatment of RP patients with mutations in exon 13 of the USH2A gene, and disease management is supportive. In addition, these patients usually receive genetic counselling on the risks of passing the condition on to their children and regular medical follow up. They also may receive adaptive support when necessary. Therefore, a significant unmet medical need exists in this sight-threatening condition.

The high unmet medical need in this orphan, sight-threatening condition warrants therapeutic intervention in those patients with usually preserved central vision. In addition, subjects with sufficient residual retinal photoreceptors translated in preserved central VF may derive a clinical benefit (see inclusion criteria of clinical study protocol).

The design of this study has been selected to provide a sufficient benefit-risk ratio to justify the participation of patients. Planned doses are expected to result in retinal concentrations in the efficacious range. In addition, multiple measures are incorporated to ensure the safety of participating subjects.

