6.1.2 Placebo

for additional details.

No placebo is used.

6.1.3 **Study Drug Shipment and Storage**

Please refer to the Pharmacy Manual and Study Reference Manual for details on shipment, storage, handling, preparation, and administration.

6.1.4 **Study Drug Accountability and Reconciliation**

The Investigator must designate a research pharmacist or other staff member to maintain an inventory record of drugs received and dispensed. Additional details on study drug handling are provided in the Pharmacy Manual and the Study Reference Manual.

6.1.5 **Dosage and Administration**

The study eye is the study/treatment eye as defined in the preceding QR-421a study; the fellow eye is the fellow/contralateral eye as defined in the preceding QR-421a study. In general, QR-421a will be administered as a 180 µg loading dose on day 1, followed by 60 µg maintenance doses at 6-month intervals. Modifications for individual participants, defined based on the dosing and/or timing of their participation completion in the previous QR-421a study are outlined below

ProQR Therapeutics Page 30 of 65

Investigational Product: QR-421a Protocol No. PQ-421a-002 (Version 4)

ProQR Therapeutics Page 31 of 65 24 May 2022

Investigational Product: QR-421a Protocol No. PQ-421a-002 (Version 4)

ProQR Therapeutics Page 32 of 65 24 May 2022

QR-421a will be administered via IVT injection in accordance with the procedures outlined by the American Academy of Ophthalmology (Avery 2014). The pharmacist (or other personnel qualified to prepare study drug for administration) at each study center will receive study drug and will prepare and/or dilute the study drug with sterile solvent (PBS) when necessary, according to the Pharmacy Manual for each administration.

Administration of study drug will only be performed by qualified ophthalmologists in an inclinic setting. No other medications should be mixed with study drug. Reference is made to the Pharmacy Manual and Study Reference Manual for detailed instructions on the IVT injection.

6.2 **Concomitant Medications and Auxiliary Therapy**

6.2.1 **Prohibited Concomitant Medications**

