7.1 Visit and Assessment Windows

For those procedures for which a specific time point post dose is required (eg, systemic exposure blood draws), the protocol refers to nominal times. Actual times for such assessments are to be recorded in the source documentation and in the eCRFs, and if any time points are missed, the

ProQR Therapeutics Page 34 of 65 reasons are also to be recorded. For more details, please refer to the case report form completion guidelines.

Subjects in the preceding QR-421a study who have completed the EOS visit as part of study completion/early termination procedures may have the Screening/Day 1 visit for this study combined with the EOS visit. All Screening/Day 1 assessments should take place during the EOS visit of the preceding study. If this is not possible, a separate Day 1 should be performed within 12 weeks of the EOS visit. If more than 12 weeks elapse from the EOS visit in the preceding study, a new Screening and Day 1 visit must be performed. Screening and Day 1 may be conducted as a single visit or as two separate visits (within 12 weeks), as per the Investigator's discretion.

Subjects in a preceding QR-421a study who did not complete an EOS visit must have a Screening and Day 1 visit performed as part of PQ-421a-002. Screening and Day 1 may be conducted as a single visit or as two separate visits (within 12 weeks), as per the Investigator's discretion.

During the Screening/Day 1 visit, subjects will be assessed according to the eligibility criteria.

Dosing day visits have a visit window of \pm 30 days. Study center phone calls to the subjects will occur 1 and 7 (\pm 3) days post-IVT injection. All visits and/or assessments can be completed over multiple, non-consecutive days.

All visit windows should be calculated from Day 1 in this study.

7.2 **Dosing and Follow-up Visits**

Dosing visits occur on Day 1, and then every 6-month for the fellow eye. Dosing visits for the study eye will begin at Month 3 or Month 9 (see Section 6.1.5 on dosing schema by participant and preceding QR-421a study), and then every 6-month. The (eventual) between-eye interval of every 3 months could be adapted in agreement with the Medical Monitor if safety data are supportive, and for logistic reasons.

Subjects should be monitored for safety, including IOP, optic nerve swelling and signs of inflammation during the post-injection period.

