5.5. Study Population

5.5.1. Subject Disposition

Subject disposition, including the number of screened subjects, the number of subjects failed screening, the number of randomized subjects, the number of subjects who received study treatment in the TE, the number of subjects who received study treatment in the CE, who completed the study and the number of subjects who discontinued from the study, along with the reasons will be summarized by treatment group.

A listing of subject disposition will be generated, including the reason for premature study or treatment discontinuation, if applicable.

A listing of screen failure data will also be provided.

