5.6. Safety – Adverse events

A treatment-emergent AE (TEAE) is defined as an event that was not present prior to administration of the dose of study drug (ultevursen or sham-procedure) and present after the dose or if it represents the exacerbation of an event that was present prior to the dose.

Adverse events will be summarized by treatment group separately as follows:

- For non-ocular AE:
 - by subject, therefore, in any tabulation, a subject contributes only once to the count for a given adverse event (System Organ Class [SOC] or Preferred Term [PT]); and
 - During the overall study period (i.e., up to the last visit for the last subject).
 - Time to onset will be calculated in hours, relative to the last dose received, irrespective of which eye received the last dose (i.e., TE or CE).
- For ocular AE:

- by eye frequencies, separately for the TE and the CE, therefore, in any tabulation, an eye contributes only once to the count for a given AE (by SOC or PT). AEs that are reported in both eyes (i.e., OU) will be reported individually by eye in the tabular summaries; and
- During the overall study period (i.e., up to the last visit for the last subject).
- Time to onset will be calculated in hours, relative to the last dose received in the eye experiencing the ocular AE.

Unless otherwise stated, any summary of any type of TEAEs which includes the SOC and PT of the events will order the SOC and the PTs within the SOC by descending incidence of PT.

The following summary tables will be produced separately according to the type of AEs (ocular/non-ocular where applicable) as defined above:

- Overview of Ocular Adverse Events for Treatment Eye during the overall study period (Safety Population)
- Overview of Ocular Adverse Events for Contralateral Eye during the overall study period (Safety Population)
- Overview of Non-Ocular Adverse Events during the overall study period (Safety Population)
- Summary of Ocular Treatment-Emergent Adverse Events for Treatment Eye during the overall study period by MedDRA System Organ Class and Preferred Term (Safety Population)
- Summary of Ocular Treatment-Emergent Adverse Events for Contralateral Eye during the overall study period by MedDRA System Organ Class and Preferred Term (Safety Population).
- Summary of Non-Ocular Treatment-Emergent Adverse Events during the overall study period by MedDRA System Organ Class and Preferred Term (Safety Population).
- SAEs
- AESIs

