6. CHANGES TO PLANNED ANALYSES

As the study is prematurely stopped by Sponsor's decision, no formal statistical analysis will be produced. Only disposition, demographic and baseline characteristics, and overview of AEs will be summarized in tables. By-subjects data listings will be produced based on raw data.

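### Does pooling one-eye and two-eye subjects distort the non-ocular time to onset?

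*SAP*

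**What the plan says.** **Grouping.** SAP 3.3 assigns subjects by regimen received: "Subject-level analyses will include subjects who received the specified treatment in either eye". A subject dosed in one eye and a subject dosed in both can share a column. The 60/60 group has the same either-or-both rule (leaving out anyone who ever had the 180/60 regimen), and the all-subjects column mixes them as well.

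**Clock.** For non-ocular events, SAP 5.6 counts hours "relative to the last dose received, irrespective of which eye received the last dose". For ocular events it counts "relative to the last dose received in the eye experiencing the ocular AE".

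**Dosing schedule.** Protocol 7.2 doses the fellow eye on Day 1 and every 6 months, and starts the study eye at Month 3 or Month 9 with the same spacing. It adds that the eventual "between-eye interval of every 3 months could be adapted in agreement with the Medical Monitor". Protocol 4.2 leaves dosing of both eyes to a decision for each subject. Protocol 6.1.5 refers to "Modifications for individual participants, defined based on the dosing and/or timing of their participation completion in the previous QR-421a study", but those details are not visible in the public text.

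**Follow-up.** Protocol 7.3 places the end-of-study visit 12 months after the last dose. Protocol 9.3.1 collects AEs at least until that visit.

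**Output.** SAP 5.5.1 counts "the number of subjects who received study treatment in the TE, the number of subjects who received study treatment in the CE", and SAP 5.7 lists dosing for each eye and all AEs. After the early stop, SAP 6 limits the summaries: "Only disposition, demographic and baseline characteristics, and overview of AEs will be summarized in tables". The shells are in a separate document (SAP 8).

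**The concern.** A second-eye injection restarts the non-ocular clock, so time to onset depends on how many eyes a subject has had dosed, whether or not the drug causes anything. SAP 5.6 describes this quantity under AE summaries by treatment group, and SAP 3.3 lets the mix of one-eye and two-eye subjects within a group vary. No AE output named in the SAP is split by eyes dosed.

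Incidence and severity of non-ocular AEs is a primary endpoint, and Protocol 9.2.2 makes timing relative to dosing part of the causality guideline. A reader could take a short group mean as a sign of a drug effect when it only reflects more frequent injections. The ocular rule avoids this, which makes the non-ocular rule look like an oversight.

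**Working it through.** The documents give no expected time to onset, so there is no figure of the plan's to reproduce. The check asks how far the mean would move with no drug effect.

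**Assumptions.** Non-ocular AEs occur at a constant rate unrelated to dosing, injections are on schedule, and 1 month = 730.5 h.

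**Formula.** An event falling at random in a gap of length g is on average g/2 from the dose that opened it. Hence mean time since last dose = Σ(g²/2) / Σg.

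**Step 1: 12 months on dosing, no follow-up after it (Protocol 7.2).**
- Fellow eye only, doses at 0, 6: (18 + 18)/12 = 3.0 months (2,192 h).
- Both eyes, second from Month 9, doses at 0, 6, 9: (18 + 4.5 + 4.5)/12 = 2.25 months (1,644 h), down 25%.
- Both eyes, second from Month 3, doses at 0, 3, 6, 9: 4 × 4.5/12 = 1.5 months (1,096 h), down 50%.

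The share of events within 1 month of a dose is 2/12 = 17%, 3/12 = 25% and 4/12 = 33%.

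**Step 2: the same doses, followed to the end-of-study visit (Protocol 7.3).** The last gap is 12 months for everyone and adds 144/2 = 72.
- Fellow eye only, visit at Month 18: (18 + 72)/18 = 5.0 months.
- Month 9 start, visit at Month 21: (18 + 4.5 + 72)/21 = 4.5 months, down 10%.
- Month 3 start, visit at Month 21: (3 × 4.5 + 72)/21 = 4.07 months, down 19%.

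The shares within 1 month of a dose become 2/18 = 11%, 3/21 = 14% and 4/21 = 19%. A longest gap of 6 months for one eye against 3 months for two therefore holds only while dosing continues. Over the whole study it is 12 months in both cases.

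**Step 3: the anticipated 24 months of dosing, plus follow-up.**
- Fellow eye only: (3 × 18 + 72)/30 = 4.20 months.
- Month 9 start: (18 + 5 × 4.5 + 72)/33 = 3.41 months, down 19%.
- Month 3 start: (7 × 4.5 + 72)/33 = 3.14 months, down 25%.

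**Step 4: pooling.** Take 20 subjects (the number the synopsis gives for the preceding study), half of them dosed in both eyes, on the step 1 values. The pooled mean is (10 × 3.0 + 10 × 2.25)/20 = 2.63 months or (10 × 3.0 + 10 × 1.5)/20 = 2.25 months. With no second eye dosed it stays at 3.0. Before the second eye starts, the schedules do not differ at all.

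**Step 5: was a second eye reached?** The documents do not settle this. Protocol 2.2.2 says of the preceding study that "the final participant visit was in Q4 2021". Counting from 1 October or 31 December 2021 to the shell document's date, 19 October 2022, gives 383 or 292 days, and Month 9 is about day 274. A second-eye dose was therefore possible. But the first date is not a Helia start date and the second is not a dosing cut-off, so this is no bound on the number of such subjects.

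**Step 6: where would the shift appear?** The tables named in SAP 5.6 are AE overviews, TEAEs by system organ class and preferred term, SAEs and AESIs. None is titled time to onset, and no mean or median of it is specified anywhere. SAP 6 narrows the tables further. In a listing, each event carries its own correct number of hours and nothing is averaged.

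**The case for a change.** The strongest case for acting is that SAP 5.6 defines the quantity under by-group summaries, the effect is pure arithmetic, and readers of safety data do look at time since dose. Neither the disposition counts nor the per-eye listings show non-ocular events by eyes dosed at onset; a reader would have to link them by hand. A derived date for each subject and one small tally would cost little and need no new data.

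The mechanism and the arithmetic stand. Four things weaken the rest.

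- The cause is the either-eye origin in SAP 5.6 combined with the stagger. It touches every subject-level column, so regrouping under SAP 3.3 is not the point.
- The either-eye origin is a reasonable choice. A systemic event may follow an injection in either eye, and a subject injected more often really is closer to a dose.
- Causality under Protocol 9.2.2 is judged by the Investigator for each event, not read from a group mean.
- A tally by eyes dosed would not compare one eye with two, because two-eye time always comes later in the study. With about 20 subjects from the preceding study and an early stop, it could be nearly empty.

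**Conclusion.** No change to the plan is needed. If non-ocular time to onset were averaged, the mean in subjects dosed in both eyes would be shorter with no drug effect: by 25% to 50% over 12 months of dosing, by about 10% to 19% once follow-up to the end-of-study visit is counted with the same doses, and by nothing if no second eye was dosed. These figures rest on a constant event rate, on-schedule injections and full follow-up; actual follow-up and the number of two-eye subjects are not stated.

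The visible plan specifies no such average. The listed hours are right event by event, and AE counts and percentages do not use this clock. SAP 6 rules out formal statistical analysis, so no test is affected. What remains is a caution for reading. If the shells do contain a summary, a footnote saying that the value depends on the number of eyes dosed by then is ordinary reporting practice and needs no amendment.
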